5.3. Efficacy/Effectiveness Endpoint(s)

Variable	Operational definition
Real-world progression-free survival	
Time in months from the initial endocrine-based therapy to the first progression or censoring date will be calculated.
 
For the purpose of this study, lines of therapy will be defined as the following Progression-based lines, in which a disease progression must occur for a new regimen to be interpreted as a new line of therapy.
 
Event: Any death or disease progression. Disease progression is taken to have occurred when a pathology report or radiological scan indicates disease progression and/or there is a physician progress note consistent with that determination. If patients did not die or have disease progression, they were censored at their last visit date during the study period for patients with only one line of therapy.

Overall survival	
Time in months from the initial endocrine-based therapy to death due to any cause or censoring date will be calculated.
 
Event: Any death recorded in the data extract. Patients who did not die will be censored at the time of data cutoff (assuming this is the last date the SSDI is searched).

Real-world tumor response	
Real-world tumor response (rwTR) will be assessed as best overall response for each regimen received within the initial endocrine-based therapy.
 
Responses will be classified as Complete response (CR); Partial response (PR); Stable disease (SD); Progressive disease (PD); Not evaluable (NE); or Undocumented. The date of the first positive response (CR or PR) and of the best overall response for each regimen will be collected.

Response rate	
The number of patients with complete response or partial response divided by the number of patients with at least one tumor assessment while on the initial endocrine-based therapy.

PFIZER CONFIDENTIAL

Time to first positive response	Months from the start date of the initial endocrine based therapy to the date of the first positive response (CR or PR).
Duration of response	Month from the date of the first positive response (CR or PR) to the date of first PD assessment or death. Patients without a PD assessment or death are censored at the the data cutoff date.
Duration of initial endocrine-based treatment	Months from the start date of the initial endocrine-based therapy to the end date of the initial endocrine-based therapy.
Duration of all treatment	Months from the start date of the initial endocrine-based therapy to the end date of the last line of treatment. Patients who are still receiving the initial endocrine-based therapy at the data cutoff date will be censored.
Duration of follow-up	Months from the index date to the date of death, or the data cutoff date, whichever came first. Patients who did not die will be censored at the data cutoff date

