9.3. Variables

9.3.1. Regimens and Lines

For purposes of this study, a regimen will be defined as one or more anti-cancer agents given in combination, over a period of time, in which the following conditions hold:

1. All agents start within 60 days of the start of the first agent in the combination, unless the start of an agent later than 60 days after the start of the first agent is specifically indicated as planned at the time of the start of the first agent.
2. No agent is discontinued and replaced by another agent within 60 days of the start of the first agent in the combination.
3. No agent is held and then resumed after an interval of more than 63 days.

Accordingly, unless the record indicates a planned delay in the start of an agent, the addition of a new agent to an existing therapy more than 60 days after start of the regimen constitutes a change of regimen. Holding of an agent for a brief period is not interpreted as a change of regimen. However, the resumption of an agent that is held and then resumed after an interval of more than 63 days is interpreted as signaling a new regimen. Discontinuation of one agent

being used in combination at any point by itself does not signal end of a regimen unless it is the only agent being administered. Occurrence of a disease progression does signal the end of a regimen. After a progression, a treatment being given before the progression will be interpreted as a new regimen—albeit identical to the previous one. This scenario, treatment through progression, occurs in some settings, and is identifiable in study data with the coding rules described here.

For the purpose of this study, lines of therapy will be defined as the following *Progression-based* lines, in which a disease progression must occur for a new regimen to be interpreted as a new line of therapy.

Disease progression is taken to have occurred when a pathology report or radiological scan indicates disease progression and/or there is a physician progress note consistent with that determination. If the radiological scan did not agree with the physician notes, the event will be determined by physician notes.

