9.3.2. Curated Data

Data abstracted by Clinical Research Nurses (CRNs) will include the following:

1. Race/Ethnicity.
2. Date of initial diagnosis of breast cancer.
3. Stage at initial diagnosis of breast cancer.
4. Modalities of treatment received at any point prior to A/MBC diagnosis (Surgery, Radiation, Chemotherapy, Hormone therapy). This variable will be collected as “Yes” or “Not Documented” for each modality. The last date of systemic therapy, including hormonal therapy, administered in the adjuvant setting prior to stage IV/MBC diagnosis will be documented, if applicable.
5. Among patients who have a record of hormone therapy prior to A/MBC diagnosis, the name(s), and start and end dates of the hormonal agents received in the adjuvant setting will be collected.

6. Status of the patient as having progressed at any point after initiation of the first hormone therapy in the adjuvant setting, prior to A/MBC diagnosis (Y/N). If yes, the date of first disease progression/recurrence following initiation of hormone therapy in the adjuvant setting will be collected.
7. Date of A/MBC diagnosis. This date defines the index date for the study, as referenced below in describing other study variables.
8. Stage at index date (IIIB, IIIC, or IV).
9. For patients documented as Stage IIIB or IIIC at index date, the date of Stage IV/metastatic diagnosis will be collected, if applicable, from the index date through the end of the record or the end of the study, whichever occurs first.
10. Sites of distant metastasis at index date, if applicable (Bone; Chest Wall; Contralateral Breast; Distant Lymph node(s); Liver; Lung; Peritoneum; Pleural nodules; Malignant pleural effusion; Skin; Brain; Undocumented; Other, Specify).
11. Disease histology (Adenoid cystic; Cribriform; Ductal; Inflammatory; Intraductal; Lobular; Medullary with lymphoid stroma; Medullary, NOS; Mucinous; Paget's disease and infiltrating; Paget's disease and intraductal; Papillary; Secretory; Squamous cell; Tubular; Undifferentiated; Undocumented, Other, specify) nearest in time to index date.
12. ER status nearest in time to index date.
13. PR status nearest in time to index date.
14. HER2 status nearest in time to index date.
15. Menopausal status (Pre, Peri, Post, UD) nearest in time to the date of, but before, index date. Date of documentation will be collected.

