16. ECOG/performance status, if available or indication of impaired performance status not otherwise classified as an ECOG rating, at index date (± 60 days). Where available, Karnofsky performance status will be converted to corresponding ECOG score.
17. Comorbidities, indicated as present vs. not indicated as present at index date. The conditions and date of the condition to be assessed will include those assessed as part of the standard Charlson Comorbidity Index. These include myocardial infarction, congestive heart failure, peripheral vascular disease, cerebrovascular accident, hemiplegia, chronic obstructive pulmonary disease, ulcer disease, diabetes, renal disease, connective tissue disease such as rheumatoid arthritis or lupus, Alzheimer's or other dementia, cirrhosis or other serious liver disease, leukemia, lymphoma, metastatic solid tumor (other than breast cancer), and HIV/AIDS.

PFIZER CONFIDENTIAL

18. Other comorbidities of interest, indicated as present vs. not indicated as present at index date: hypertension and hyperlipidemia.
19. Dates of disease progression after index date through the end of the record or the end of the study, whichever occurs first.
20. Documentation of treatment modifications (dose modification, schedule changes, dose delay, hold, or discontinuation) for palbociclib, **CCI** [REDACTED] and reasons for treatment modifications, if applicable, from the index date through the end of the record or the end of the study, whichever occurs first. Date of treatment modification and reason for modification will be collected, if available.
 - Reasons for modification will include: Cost, disease progression, patient refusal/request, toxicity (specify), other (specify), or UD.
21. Oral anti-cancer therapies. This will include all treatments from the index date through the end of the record or the end of the study, whichever occurs first. **CCI** [REDACTED]
22. Documentation of any IV, IM, or subcutaneous anti-cancer therapy not otherwise documented in standard medication tables, including all treatments received from the index date through the end of the record or the end of the study, whichever occurs first. Agent and start and end dates will be collected.

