9.3.4. Derived Variables

Variables suggested to be derived for this study's purpose will be generated by Pfizer analytical team. Final algorithm to derive the variables will be further determined by Pfizer. The suggested variables derived from abstracted and extracted data will include the following:

1. Age at index date, at initiation of the earliest endocrine-based regimen, and at first treatment regimen after the index date.
2. Weighted index of comorbid disease condition. Weighting of comorbid conditions (not including breast cancer) will follow the weighting as specified in the Charlson Comorbidity Index.
3. Start and end dates of anti-cancer treatments from the index date through the end of the record or the end of the study, whichever occurs first.
4. Treatment regimens, derived from oral and infused agents delivered, including start and end dates.
5. Endocrine sensitivity prior to the index date, defined as endocrine sensitive vs. resistant vs. refractory based on adjuvant endocrine therapy experience. Endocrine sensitive: ≥24 months without recurrence/progression after completion of endocrine therapy in the adjuvant setting; Endocrine resistant: recurrence/progression after completion of endocrine therapy, and within 24 months of completion of endocrine therapy; Endocrine refractory: recurrence/progression while on endocrine therapy in the adjuvant setting, defined as occurring while on or within <30 days after discontinuation of endocrine therapy. The 30 day window allows that endocrine therapy may be discontinued because of a perceived progression before that progression is actually documented.
6. Primary endocrine resistance defined as a relapse while on the first 2 years of adjuvant endocrine therapy or disease progression within the first 6 months of first-line endocrine therapy for A/MBC, while on endocrine therapy.

PFIZER CONFIDENTIAL

7. Secondary (acquired) endocrine resistance defined as a relapse while on adjuvant endocrine therapy but after the first 2 years or a relapse within 12 months of completing adjuvant endocrine therapy, or disease progression ≥ 6 months after initiating endocrine therapy for A/MBC, while on endocrine therapy.

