4.1.1. Inclusion criteria

Patients must meet all of the following inclusion criteria to be eligible for inclusion in the study:

1. *Female or male sex.*
2. *Diagnosis (confirmed by clinical review) of A/MBC, defined as breast cancer at stage IIIB, stage IIIC, stage IV or identified as having distant metastasis.*
3. *Age ≥ 18 years at A/MBC diagnosis.*
4. *Initiated a CDK4/6i in combination with an AI as initial endocrine-based therapy after A/MBC diagnosis on or after 2/3/2015 and before 4/1/2019.*
 - *Note that the date of the start of the inclusion period reflects the month that the first CDK4/6i (ie, Palbociclib) received U.S. FDA approval.*
5. *Evidence of ER or PR positive disease, or absence of any indication of ER and PR negative disease closest to A/MBC diagnosis (ie, patients are eligible without affirmative indication of ER/PR+ status as long as ER/PR- indication is not present).*
6. *Evidence of HER2 negative disease, or absence of any indication of HER2 positive disease closest to A/MBC diagnosis (ie, patients are eligible without affirmative indication of HER2- status as long as HER2+ indication is not present).*

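### SAP 5.3 has no rule to stop a progression that prompted CDK4/6i + AI, but was documented on or just after the start date, from counting as an rwPFS event

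*SAP*

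**What the plan says.** SAP 5.3 defines the rwPFS interval: "Time in months from the initial endocrine-based therapy to the first progression or censoring date will be calculated". The event is equally broad: "Event: Any death or disease progression".

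The progression field that feeds it is item 19 of Protocol 9.3.2: "Dates of disease progression after index date through the end of the record or the end of the study, whichever occurs first". The index date is not the start of therapy. Item 7 of the same section reads: "Date of A/MBC diagnosis. This date defines the index date for the study, as referenced below in describing other study variables".

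The eligibility rule in SAP 4.1.1 is "Initiated a CDK4/6i in combination with an AI as initial endocrine-based therapy after A/MBC diagnosis on or after 2/3/2015 and before 4/1/2019". It sets no upper limit on the gap between diagnosis and start, and the therapy need only be the first endocrine-based one, not the first systemic one. Item 9 of Protocol 9.3.2 foresees stage change after the index date: "For patients documented as Stage IIIB or IIIC at index date, the date of Stage IV/metastatic diagnosis will be collected, if applicable".

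Under Protocol 9.3.1, progression may rest on pathology, or on a "radiological scan indicates disease progression and/or there is a physician progress note consistent with that determination". Physician notes prevail where scan and notes disagree. No rule says which date applies when several documents describe one event. The same section makes progression end a regimen, and treatment continued unchanged afterwards counts as a new regimen.

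Protocol 9.3.4 item 5 allows for late documentation in one place only. It gives a 30-day window for adjuvant endocrine-refractory status because "endocrine therapy may be discontinued because of a perceived progression before that progression is actually documented".

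**The concern.** The rwPFS clock starts at therapy, but the progression record starts at diagnosis, and the date attached to a progression is the date of a document. If the treating physician acts on a suspected progression and the report or note follows some days later, the date falls after the start. The definition cannot tell that entry from a failure of the new treatment.

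rwPFS for Palbociclib + AI is a primary outcome under Objective 2. Each such patient adds a false step near time zero, always in the direction of shorter rwPFS. The same entry ends the regimen under Protocol 9.3.1. Response is abstracted only to the end of the first progression-based line (Protocol 9.3.2 item 23), so a later response in that patient might not be collected. That is a reason to settle the rule before curation.

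**Working it through.** **1. Reading the definition.** Neither document requires an rwPFS progression to be new relative to a baseline assessment, sets a minimum interval after start, or says how to treat a progression dated on the start date.

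**2. Worked case.** A patient is stage IIIB at index. Palbociclib + AI starts on day 0. A scan report and note recording progression are dated day 6. The rule gives an event at 6/30.4375 = 0.2 months.

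**3. Size.** The plan gives no rwPFS projection to reproduce. Its one derived figure, average follow-up, does reproduce: 49.9/2 + 8.0 = 32.95 months, against 33 stated in Protocol 9.5. Nothing below depends on it.

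Inputs:
- Median 24.5 months: Protocol 7, cited real-world study of palbociclib + letrozole.
- 12-month progression-free rate 84.1%: Protocol 7, cited chart review of palbociclib + AI.
- Cohort 1100 to 1300: Protocol 9.5, all CDK4/6i + AI patients.
- Share p with a false event near time 0: not in the documents; assumed 1% to 10%.

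The observed curve is (1 − p)·exp(−λt), with λ = ln 2/24.5 = 0.0283 per month. Setting it to 0.5 gives median = 24.5 × ln(2(1 − p))/ln 2. The 12-month rate becomes 84.1 × (1 − p).

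| p | Patients of 1100–1300 | Median (months) | Shift (months) | 12-month rate |
|---|---|---|---|---|
| 0 | 0 | 24.5 | 0 | 84.1% |
| 1% | 11–13 | 24.1 | −0.4 | 83.3% |
| 2% | 22–26 | 23.8 | −0.7 | 82.4% |
| 5% | 55–65 | 22.7 | −1.8 | 79.9% |
| 10% | 110–130 | 20.8 | −3.7 | 75.7% |

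A Kaplan-Meier simulation (n = 1200, follow-up uniform on 8 to 58 months, false events spread over the first month, 300 runs) gave mean medians of 24.6, 23.9, 22.7 and 20.9 months at p = 0, 2%, 5% and 10%, in line with the formula.

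**4. Against sampling error.** Under the same assumptions, SE(median) = √(I/n)/λ, where I is the integral from 0 to 24.5 of λ/(S(u)G(u)). Here G(u) = 1 up to 8 months and (58 − u)/50 after that. For n = 1200, SE = 1.105 and the 95% interval is 24.5 ± 1.96 × 1.105, or 22.3 to 26.7 months. The 5% case (22.7) lies inside it.

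**5. What a window would set aside.** Under the same exponential curve, the share of true events (deaths included) in the first 14 days is 1 − exp(−0.0283 × 0.460) = 1.3%. In the first 30 days it is 1 − exp(−0.0283 × 0.986) = 2.7%. Progressions among these are delayed to their next documentation. The median moves only if that comes after the median, or the patient is censored first.

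**The case against.** The strongest reply is that the definition already presupposes a later event and that the exposed group is small. Much of this stands.

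- **Progression dated before start.** A reader might infer that the literal first abstracted date would produce negative rwPFS times. The documents do not support that as the intended reading. Time runs from therapy start, and the progression-based lines in Protocol 9.3.1 put a clearly earlier progression in an earlier line. Such a progression is implicitly outside the endpoint, though saying so would cost nothing.
- **Narrow exposure.** Where the A/MBC diagnosis itself prompted treatment, that diagnosis is the index date, and only later-dated documents about the same event are at risk. Conversion to stage IV also has its own date field, and nothing says curators would enter it a second time as a progression.
- **Line-1 duration.** A reader might infer that first-line duration collapses to days for every affected patient. That fails for progression on earlier chemotherapy documented after the switch. No progression then separates the two regimens, so both sit in one line, and the sequence duration in SAP 5.2 would include the chemotherapy months.
- **The 30-day window.** It concerns stopping adjuvant therapy. It shows that the sponsor recognises documentation lag; it is not a precedent for a rule at the start of study therapy.
- **Curation specifications.** Protocol 9.6.1 mentions specifications from the sponsor that are not among the documents. They might contain a rule. The endpoint definition in the SAP would still need to state it.

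What survives is the prompting progression documented on or shortly after the start. Nothing in either document removes it from rwPFS.

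**Conclusion.** The gap is real but limited. Read as written, SAP 5.3 turns a prompting progression documented on or just after day 0 into an almost immediate rwPFS event, and Protocol 9.3.1 ends the regimen with it. The error runs in one direction, against the treatment.

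Its size is unknown because the documents give no frequency. On an exponential curve with a 24.5-month median, the reported median falls by about 0.4 month at 1%, 0.7 at 2% and 1.8 at 5%. These are illustrations of an assumed share, not estimates for this dataset. The patient counts refer to the whole cohort, since the size of the Palbociclib + AI group is not given. A shift up to the 5% case would lie within the sampling interval for the median. That limits its weight in a descriptive study without hypotheses, but a one-directional error does not shrink with sample size. The documents do not support the stronger inference that rwPFS is materially biased; they support only that it could be, with no rule to prevent or measure it.

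**What to change.** In SAP 5.3:

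1. State that rwPFS events must be dated after the start of the initial endocrine-based therapy.
2. Prespecify a short window after start within which a documented progression is treated as baseline disease. Deaths in the window still count. The length is a convention: 14 days is one choice, and 30 days would match the only documentation-lag window in the protocol. Neither is derived from data in the documents, so the SAP should say that it is a convention.
3. Report how many progressions are set aside.
4. Repeat rwPFS counting all progressions dated after day 0.

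Keep the change to rwPFS. If the same rule is to govern regimens and lines, Protocol 9.3.1 must be amended to match, because it makes any progression end a regimen. The sponsor should also record whether the rwPFS change counts as a major modification of a primary endpoint under Protocol 9.7.

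The cost is a short addition to the SAP, one count and one further run. The downside is that a true progression inside the window is counted only when next documented, a slight upward bias. On the exponential illustration, the share of events exposed to this (1.3% at 14 days, 2.7% at 30 days) is similar to the smaller assumed carry-over shares, so the shorter window costs less and the sensitivity run is needed to show the effect of the choice.

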9.3.3. Extracted Data

Patient data from OncoEMR will be flagged to be excluded from the regulatory study. Data extracted from the Definitive Oncology Dataset through SQL query will include the following:

1. Sex.
2. Insurance status (private only, public only, public and private, or neither) at index date and at initiation of the earliest endocrine-based regimen after the index date.
3. Date of birth.

[figure not shown]
4. Date of death, as indicated in the clinical record and by Social Security Death Index (SSDI) records or associated obituary records linked to the Definitive Oncology Dataset.
5. Treatments and dates of treatments for all infused or injected anti-cancer therapies from the index date through the end of the record or the end of the study, whichever occurs first.

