5. ENDPOINTS AND COVARIATES

- Index date:** Date of A/MBC diagnosis.
- Observation period:** February 3, 2015 through the data cutoff date (end of data curation). Since data curation will start in November 2019, this allows patients to have a potential follow-up of at least 6 months.
- Follow-up:** Patients will be followed from the index date to the data cutoff date, or death, whichever comes first.

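### OS censors every patient without a recorded death at data cutoff, which assumes complete death capture to that date, and the readable SAP neither documents nor tests that assumption

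*SAP*

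**What the plan says.** OS is one of the clinical outcomes of primary Objective 2. SAP 5.3 defines it thus: "Time in months from the initial endocrine-based therapy to death due to any cause or censoring date will be calculated". The event is "Event: Any death recorded in the data extract", and the censoring rule is "Patients who did not die will be censored at the time of data cutoff (assuming this is the last date the SSDI is searched".

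Protocol 9.3.3, item 4, names the sources: "Date of death, as indicated in the clinical record and by Social Security Death Index (SSDI) records or associated obituary records". SAP 5 sets the observation period as "February 3, 2015 through the data cutoff date (end of data curation", so cutoff follows the end of curation. Neither document gives the date of the last SSDI or obituary search.

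Duration of follow-up in SAP 5.3 uses the same convention: "Patients who did not die will be censored at the data cutoff date". For rwPFS, patients without progression or death are handled differently: "they were censored at their last visit date during the study period for patients with only one line of therapy".

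SAP 6 and 7 plan one unadjusted Kaplan-Meier analysis of OS, with no imputation and no covariates. The shells for Tables 7a and 7b hold events, censored patients and one median. Protocol 9.9 (limitations) does not mention death capture.

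**The concern.** A patient who leaves the practice and dies without the death reaching the chart, the SSDI or an obituary is analysed as alive until cutoff. That patient contributes no event and stays in the risk set to the end, so the error has one direction: OS looks longer.

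The SAP states its assumption, which is to its credit, but nothing planned would show a reader whether it held. Duration of follow-up does not help, because a patient last seen years before cutoff is also counted there as followed to cutoff. With a single OS estimate, a reader cannot tell a long median from a median lengthened by missed deaths.

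**Working it through.** **Inputs from the documents.** Treatment starts from 2/3/2015 to before 4/1/2019 (Protocol 9.2.1). Data collection is assumed to start by 12/1/2019, and average follow-up is given as 33 months (Protocol 9.5). Published OS in HR+/HER2- disease is 38.5 to 60.1 months (Protocol 7).

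**Reproducing the plan's figure.** 2/3/2015 to 4/1/2019 is 49.9 months, and 4/1/2019 to 12/1/2019 is 8.0 months. 49.9/2 + 8.0 = 32.95, against 33 stated. Maximum follow-up is 49.9 + 8.0 = 57.9 months. The documents state no OS estimate, event count or capture rate.

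**Assumptions.** Exponential survival with hazard ln 2 / median, uniform entry over 49.9 months, and cutoff 8.0 months after the last entry. True medians are 38.5, 48 (an assumed value within the protocol's range) and 60.1. Results are Kaplan-Meier estimates on 300,000 to 400,000 simulated patients.

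**Direction.** The estimate is the product of (1 - d/n) over death times. A missed death lowers d at its own time and leaves n too large afterwards. Both raise the curve.

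**Step 1: a share of all deaths is missed, SAP rule.**

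| Deaths captured | 100% | 95% | 90% | 85% | 80% | 70% |
|---|---|---|---|---|---|---|
| Median, true 38.5 | 38.4 | 41.4 | 44.9 | 49.2 | 54.4 | not reached |
| 36-month OS (%), true 38.5 | 52.2 | 54.6 | 57.0 | 59.4 | 61.7 | 66.6 |
| Median, true 48 | 48.0 | 51.7 | 56.0 | not reached | not reached | not reached |
| 36-month OS (%), true 60.1 | 65.8 | 67.5 | 69.2 | 70.9 | 72.7 | 76.1 |

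Check on the first column: 2^(-36/38.5) = 0.523, against 52.2% simulated. Missing 5% of deaths adds 41.4 - 38.4 = 3.0 months to a true 38.5 and 51.7 - 48.0 = 3.7 months to a true 48. Missing 10% adds 6.5 and 8.0 months. A true 60.1 lies beyond the maximum follow-up, so only the landmark estimate can be read.

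**Step 2: deaths are missed only after a patient leaves.** Assumed: 10% to 30% lost by 24 months (loss hazard -ln(1 - p)/24, so 0.0044 to 0.0149 per month), with 60% to 90% of later deaths found. About 1% to 9% of all deaths are then missed. A true 38.5 reads 39.0 to 44.6, an excess of 0.5 to 6.1 months. A true 48 reads 48.6 to 57.8, an excess of 0.6 to 9.8. The top value sits just under the 57.9-month maximum, so the median may simply not be reached.

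**Step 3: which sensitivity rule is usable.** Same loss model, with the last visit at, or shortly before, death, loss or cutoff.

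| Rule | True 38.5 | True 48 |
|---|---|---|
| Deaths counted to last visit + 90 days, survivors censored at last visit | 35.8 to 38.2 | 44.5 to 47.6 |
| Deaths counted and survivors censored on the same window, last contact + 90 days or cutoff | 38.2 to 39.0 | 47.7 to 48.8 |

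The first rule reads low even at full capture, because deaths count for 90 days in which survivors contribute no time. Censoring survivors at last visit while counting every late death is worse: a true 48 reads 38.8 to 45.5. The common window removes the asymmetry. Other seeds and visit gaps move these figures by a few tenths of a month.

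**Step 4: departure related to prognosis.** Assume 10% to 30% of patients stop attending 3 to 6 months before death, with 10% random loss and full capture. A row limited to deaths within 90 days, with survivors censored at last visit, then reads 41.5 to 52.0 for a true 38.5, while the SAP rule gives 38.5 to 38.6. The common window adds survivor time without adding events, so it reads at least as high.

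**The case against.** The strongest defence is that nothing in the documents says deaths are missed. Three sources are used, and with outside death linkage, censoring at the last search date is a recognised choice whose assumption the SAP states openly. This stands. A reader might infer that the planned OS is biased, but the documents support only the conditional statement, and the sizes above rest on assumed loss and capture rates. At the mild end the shift is about half a month.

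A reader might also infer that OS and rwPFS contradict each other, because rwPFS uses "they were censored at their last visit date during the study period". They do not. Progression is observed only through scans, pathology or physician notes, so the last visit is a natural limit; death can be learned outside the clinic. The rwPFS rule is also worded for patients with only one line of therapy and no event, so it is not a rule for the whole OS set.

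It is fair, too, that last-contact censoring has its own weakness: Step 4 shows it can overstate OS when patients stop attending as they decline. That rules it out as a replacement for the planned analysis, but not as a comparison beside it.

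Finally, the study is descriptive, with no hypotheses or decision rules (SAP 3.1 and 3.2). This limits the consequence, but OS remains a primary-objective outcome reported as a median with a confidence interval. Some SAP text is redacted; the methods and missing-data sections are readable and contain no alternative OS censoring.

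**Conclusion.** The point holds in conditional form. The cutoff rule is valid only with complete death capture through cutoff, the documents supply neither a completeness figure nor a linkage date, and no readable analysis tests it. The bias is zero at full capture. Under the assumed 10% to 30% loss by 24 months and 60% to 90% capture of later deaths, it reaches about 6 months on a true median of 38.5 and about 10 months on a true 48. These figures also rest on exponential survival, uniform entry and loss unrelated to prognosis; they show direction and scale and do not predict this study's result. The different rwPFS rule is not in itself an error. The remedy is worthwhile because it is cheap and leaves the planned analysis in place.

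**What to change.** 1. Keep the planned OS analysis. State the date of the last SSDI and obituary linkage, and end OS at the earlier of that date and data cutoff, counting no deaths after it.
2. Add one pre-specified sensitivity row to Tables 7a and 7b: count deaths up to last contact + 90 days, and censor all other patients at the earlier of last contact + 90 days and cutoff. Do not censor survivors at the last visit itself; deaths and survivors must share one at-risk window.
3. Report the share of censored patients last seen more than 90 days before cutoff, and the number of deaths by source.
4. State beside the row that it assumes leaving the practice is unrelated to prognosis, that it can overstate OS if patients stop attending shortly before death, and that it is read with the main result.

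Cost: a last-contact date for every patient, one Kaplan-Meier run and one table row. The date is not free: the SAP names a last visit only for part of the rwPFS set, and Protocol 9.3.2 and 9.3.3 do not list it as a variable. The OS statement may become less favourable.
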